#### **7.2.4. Infusion delays, missed doses and dose adjustment**

##### **7.2.4.1. Infusion delays and missed doses**

Every effort should be made to schedule visits within the protocol-specified windows.

In the case that an infusion cannot be administered at a scheduled visit, it has to be administered as soon as possible. If the delay is between 1 and 3 days (including), the procedures at the original scheduled time point should be performed.

If the delay is more than 3 days, the procedures at the next infusion should be performed (the infusion at the original scheduled visit will be considered a missed dose).

Patients with infusion delays > 28 days should normally discontinue treatment and enter the Follow-up Period. If the Investigator intend to continue the treatment for patients who have infusion delay >28 days, specific consultation and agreement between the Investigator and the Medical Monitor are required in setting where benefit/risk may justify continued use of Investigational Product.

##### **7.2.4.2. Dose modification for subsequent infusions**

This study allows dose adjustment for toxicities. Dose modification is based on the toxicities from previous infusions. Patients who experience reversible DLTs **are** allowed to receive

---

 Any new Grade $\geq$ 3 laboratory abnormality, such as liver function test elevations, electrolyte fluctuation, or hematologic deterioration should be assessed for potential risk to continued dosing. In the event of uncertainty, the Medical Monitor should be contacted.

additional infusions at the next lower dose level, provided that the toxicities have reverted to grade≤1 in 28 days after last infusion, and that the patients still meet the inclusion criteria for adequate organ functions. Dose modification for reasons other than toxicities is not allowed, unless it is scientifically justifiable and must be agreed by the Sponsor.

*For patients who experience DLTs, re-escalation to the dose level causing DLT is not permitted.  
Up to two dose-level reductions per patient are allowed in this study.*

#### **7.2.5. Discontinuation of patients from treatment**

Each patient has the right to withdraw from the study any time. Patients MUST discontinue Investigational Product (and non-investigational product at the discretion of the Investigator) for any of the following reasons:

- Withdrawal of informed consent (patient's decision to withdraw for any reason)
- Any clinical adverse event (AE), laboratory abnormality or inter-current illness, which, in the opinion of the investigator, indicates that continued participation in the study is not in the best interest of the patient.
- Pregnancy or beginning breastfeeding
- Termination of the study by the Sponsor
- Loss of ability to freely provide consent through imprisonment or involuntarily incarceration for treatment of either a psychiatric or physical (e.g., infectious disease) illness
- Poor compliance with protocol.
- Discretion of the investigator.
- Disease progression or clinical deterioration that no further benefit from treatment is likely (clinical deterioration should be guided by clinical observation described in Section 6.2 and Investigator's judgment).
- Dosing delays longer than 28 days

All patients who discontinue should comply with protocol specified follow-up procedures as outlined in Section 7.2.5 . The only exception to this requirement is when a patient withdraws consent for all study procedures or loses the ability to consent freely (i.e., is imprisoned or involuntarily incarcerated for the treatment of either a psychiatric or physical illness).

### 7.2.6. Replacement of participants

A patient who is withdrawn from the study before the first 4 weeks after first infusion of IP may be replaced with a new one to receive the same dose level if the withdrawal from the study is not related to treatment-emergent toxicities.

### 7.3. Follow-up period

After completion of the Treatment period, the patients will have 6 monthly follow-up visits. All patients should complete Follow-up Visit 1 ( $28 \pm 3$  days after the last dose of IP).

The procedures for the follow-up visits are as follows:

1. Physical examination
2. Vital signs
3. ECOG performance status
4. AE assessment
5. 12-lead ECG
6. CBC with differentials and D-dimer
7. Coagulation profile: PT, INR, aPTT
8. Blood chemistry profile: fasting glucose, BUN, creatinine, alkaline phosphatase, ALT, AST, total bilirubin, total protein, albumin, globulin, sodium, potassium, chloride, calcium, magnesium, phosphorus, uric acid, lactate dehydrogenase, IgG and IgM.
9. Thyroid function tests: TSH, T3 and free T4.
10. Urinalysis.
11. Urine pregnancy test for female patients with child-bearing potential
12. Concomitant medications
13. Tumor assessment: if the prior imaging studies are done more than 8 weeks ago)
14. Pharmacokinetic and pharmacodynamic studies.

If the patient refuses or is unable to attend the follow-up visit 1, the reason(s) should be noted in the patient's source documentation.

---

 Every 8 weeks.

 A positive urine pregnancy test needs to be verified by a serum beta-HCG test. Postmenopausal women must be amenorrheic for at least 12 months in order not to be considered of child-bearing potential.

 Only for follow-up visit 1.

Completion of subsequent follow-up visits (Follow-up Visits 2 and beyond) will depend on the status of the patients at the end of treatment. Except for patients who discontinue due to worsening PD, all patients will be followed from the last dose of IP for approximately 6 months until relapse, initiation of a new therapy or the toxicities stabilized or  $\leq$  grade 1. The evaluations performed during the Follow-up Visits will be recorded on the CRF.

Whether or not each patient completes the study drug treatment through the first cycle will be documented on the CRF, including how many doses in Cycle 1 were received. Patients will be considered to have completed Cycle 1 treatment if they completed 4 infusions of IP in Cycle 1 and completed all evaluations at the end of Cycle 1.

### **7.3.1. Survival follow up**

Following completion of the treatment and follow-up periods, all patients will be followed for survival after completion of treatment phases and through the follow-up period of the protocol. Patients will have their survival status assessed approximately every 3 months by either a telephone or in-person contact until study completion or termination by the Sponsor.

## **7.4. Post study access to Investigational Product**

At the end of the protocol-specific periods of active study therapy, the Sponsor will not continue to supply study drugs to the patients/investigators unless the Sponsor decide to extend the study. The Investigator should ensure that the patients receives appropriate standard care to the condition under the study.

## **7.5. Records of concomitant medications and procedures**

All medications, including pharmacologic doses of vitamins, herbal medicines, or other alternative medicine all transfusions, including blood component therapies, IV immunoglobulin, and hematopoietic growth factors administered within 28 days before first infusion are to be documented in the appropriate source documents and the CRF, along with the reason for and details of therapy use. Results of assessments must be reviewed by the safety review committee (SRC) before administering the first dose of the next cycle.

### **7.5.1. Prohibited concomitant medications and procedures**

The following medications, therapies, and procedures are prohibited during the study:

- Any investigational agent other than HLX06.

- Any anti-neoplastic treatment with activity against epithelial cancer other than investigational product.
- Radiation therapy unless for pain relief at local lesion.
- Any surgery for the management of the patient's disease, unless for life-threatening situations during treatment period.
- Thrombopoietin-mimetics.
- Myeloid growth factors to stimulate faster granulocytic recovery, unless for neutropenic fever.
- Erythropoietic agent is not permitted, except for the management of patients with treatment-emergent renal failure or those with documented low erythropoietin.
- Non-steroidal anti-inflammatory drugs (NSAIDs), unless for pain relief.
- Live vaccines are NOT allowed during the study.

### **7.5.2. Permitted concomitant medications and procedures**

**Prophylactic pre-medications:** Medications intended to prevent infusion reactions or other toxicities are permitted by previous experience with HLX06 in a patient as described in Section 6.4.

**Corticosteroid use:** Inhaled or intranasal corticosteroids (with minimal systemic absorption) may be continued if the patient is on a stable dose. Non-absorbed intra-articular corticosteroid injections are permitted. Stable corticosteroid use with less than 10 mg prednisone is permitted.

**Prophylactic antimicrobial agents:** If the patient is considered to have high-risk for infection during the study period, prophylactic antimicrobial agents are allowed until the risk is lowered. Prophylactic antibiotics are to be provided according to institutional guidelines at the study center. If no institutional guidelines exist, prophylactic antimicrobial therapy (e.g., oral fluoroquinolone [levofloxacin or ciprofloxacin] for bacterial infections, oral fluconazole for fungal infections, and oral famciclovir 250 mg twice daily or equivalent for viral infections) are allowed for high-risk patients from the start of investigational product administration until the infection risk is lowered or recovery of white blood cells (WBCs).

**Transfusion support:** The use of blood components is recommended during the study period. Packed red blood cell (RBC) transfusion is recommended for hemoglobin  $\leq 8.0$  g/dL or per institutional guidelines. Platelet transfusion is recommended for platelet counts  $\leq 20 \times 10^9/L$  or with signs of bleeding or per institutional guidelines.

**Palliative therapies:** Palliative therapies (e.g. focal radiotherapy for pain, thoracentesis, or paracentesis for comfort may be administered after consultation with the Medical Monitor.

**Vaccines:** the use of killed or attenuated vaccines for the prevention of influenza is permitted at any time without a study drug washout interval. The use of other killed or attenuated vaccines for the prevention of infectious diseases may be permitted on a case-by-case basis and must be discussed with the Medical Monitor prior to its use. A washout interval prior to and post vaccination while on study may be required in these instances. Any vaccinations given while on study must be documented in the patient's medical records and in the CRF.

All patients should be maintained on the same concomitant medications throughout the study period, as medically feasible. Any new concomitant medications prescribed for the patient or changes to dosing/schedule of concomitant medications should be recorded on the appropriate CRF page. The addition of a new concomitant medication for which there is a concern that it may not be permitted should be first reviewed with the Medical Monitor.

No concomitant medication information will be collected following patient discontinuation from the study except for concomitant medication use associated with study drug-related adverse events or adverse events that lead to discontinuation from study.

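### Section 7.5.1 bans live vaccines outright, while Section 7.5.2 permits attenuated influenza vaccine at any time and other attenuated vaccines case by case

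*Combined protocol and SAP*

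**What the plan says.** Three rules on vaccines appear in two adjacent sections of the protocol.

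- **Section 7.5.1 (prohibited).** The list opens with "The following medications, therapies, and procedures are prohibited during the study", and its last item reads "Live vaccines are NOT allowed during the study". No exception is attached.
- **Section 7.5.2 (permitted), influenza.** "the use of killed or attenuated vaccines for the prevention of influenza is permitted at any time without a study drug washout interval". No contact with the Medical Monitor is asked for.
- **Section 7.5.2 (permitted), other infections.** "The use of other killed or attenuated vaccines for the prevention of infectious diseases may be permitted on a case-by-case basis", on condition that the use "must be discussed with the Medical Monitor prior to its use". A washout before and after vaccination may be required in these cases.

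Section 7.5.2 also requires every vaccination on study to be documented in the medical record and the CRF. It closes with a general safeguard for concomitant medication: "a new concomitant medication for which there is a concern that it may not be permitted should be first reviewed with the Medical Monitor".

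**The concern.** A vaccine described as attenuated, in contrast to killed, is normally a live one. On that reading the same product is forbidden in one section and permitted in the next. The vaccine paragraph in 7.5.2 does not mention the ban in 7.5.1, so a site that looks up the permission has no prompt to look for the prohibition.

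What is at stake is patient safety and protocol compliance. A site acting in good faith on an express permission could give a patient with advanced cancer a product that the sponsor has decided to exclude, and would commit a protocol deviation in doing so. Dose escalation, the DLT definition and the analysis are not touched.

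**Working it through.** No arithmetic applies. The check is whether the two sections can be read together, and whether anything else in the document reconciles them.

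**Step 1: does the ban contain an exception?** Section 7.5.1 has nine items. Five carry their own exception: radiotherapy, surgery, myeloid growth factors, erythropoietic agents and NSAIDs. The NSAID item, for example, reads "Non-steroidal anti-inflammatory drugs (NSAIDs), unless for pain relief". The authors therefore wrote exceptions into the item where they wanted them. The live-vaccine item has none, and its negative is in capitals. An unwritten exception for attenuated vaccines cannot be inferred.

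**Step 2: what does *attenuated* mean here?** There are two candidate readings.

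- *Weakened but live.* This is the ordinary sense and the one that the contrast with *killed* implies. The two sections then conflict directly.
- *Inactivated.* The phrase would then repeat itself, since killed and inactivated mean the same. The conflict would disappear, but the word would be wrong and would need the same correction.

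The text needs correcting on either reading.

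**Step 3: compare the rules by product.**

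| Product | Section 7.5.1 | Section 7.5.2 | Consistent? |
|---|---|---|---|
| Killed influenza vaccine | Not prohibited | Permitted at any time, no washout | Yes |
| Live-attenuated influenza vaccine | Prohibited | Permitted at any time, no washout | No, and no prior check |
| Other killed vaccine | Not prohibited | Case by case, Medical Monitor first | Yes |
| Other live-attenuated vaccine | Prohibited | Case by case, Medical Monitor first | No, but with a prior check |

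**Step 4: does anything elsewhere settle it?** No other vaccine rule, definition of live or attenuated, carve-out, or statement of which section prevails was found in the document.

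**Step 5: would existing safeguards catch it?** For vaccines other than influenza, the required Medical Monitor discussion could. For influenza vaccine, only the general safeguard at the end of 7.5.2 remains. It operates when someone already doubts that the medication is allowed, and a site that has just read an express permission has little reason to doubt. Documentation in the CRF would reveal the event only afterwards.

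**Step 6: who is exposed to both rules?** Sections 3.1 and 4.1 plan a maximum of 30 patients, more if some are replaced. The Synopsis sets treatment at up to one year, extendable by arrangement with the sponsor. The ban applies for the whole study, and Section 7.3 adds about six months of follow-up. Over such a period a seasonal influenza vaccination can plausibly come up.

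**The case against.** The strongest reply has four parts.

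- **The breach is conditional.** A site giving a killed vaccine under 7.5.2 does nothing wrong; only a live-attenuated product creates the conflict. This is correct, and the conclusion is limited accordingly.
- **Safeguards exist.** Other vaccines need prior Medical Monitor discussion, and a site that has read the emphatic ban in 7.5.1 would have reason to ask about influenza vaccine too. The first half stands and lowers the risk for one of the two sentences. The second half is possible, but it relies on the site noticing a conflict that the protocol does not flag.
- **Harm is not shown.** The protocol gives no reason for the ban and does not describe HLX06 as immunosuppressive. Section 1.3.1 expects a profile like ramucirumab monotherapy, with hypertension most prominent, and entry requires neutrophils of at least 1500/mm³ and 28 days since cytotoxic chemotherapy. This limits what can be said about the size of the harm. On the other side, Section 1.3.1 calls the human toxicities unknown, Section 7.5.2 provides antimicrobial prophylaxis for patients at high risk of infection, and Section 6.4 uses corticosteroids for infusion reactions. In any case the sponsor set the ban, and a rule the sponsor thought necessary should not be undone in the next section.
- **Intent is uncertain.** The wording occurs twice with tiered conditions, so it could reflect an intended exception that was left out of 7.5.1. This is a fair point about the remedy. It does not defend the present text, because a site still cannot use the permission for an attenuated vaccine without breaching the ban.

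**Conclusion.** The concern holds. As written, live-attenuated vaccines are both prohibited and permitted: for influenza with no prior check, for other infections subject to Medical Monitor discussion. The conclusion rests on the ordinary meaning of *attenuated* when set against *killed*; if the sponsor meant inactivated, the wording is still wrong.

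The extent is two sentences in 7.5.2 against one line in 7.5.1, governing every patient in the study. The number who would actually be offered a live-attenuated product cannot be derived from the documents, and no effect on the MTD or any other estimate is claimed. It is an inconsistency in a safety instruction that should be corrected, not a threat to the primary analysis.

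**What to change.** In both vaccine sentences of Section 7.5.2, replace the killed-or-attenuated wording with *killed (inactivated)*, and add one sentence: *Live vaccines, including live-attenuated vaccines, are prohibited (see Section 7.5.1).* This follows the protocol's own ban and keeps inactivated influenza vaccine available at any time. It does close the case-by-case route for attenuated vaccines. If the sponsor wants to keep that route, or to allow live-attenuated influenza vaccine, the exception and its conditions should be written into the live-vaccine item of 7.5.1 so that the two sections agree.

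The cost is a change of wording in two sentences and one cross-reference, with no new procedure or data collection.

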### **7.5.3. Effective contraceptive measures**

For female patients of child-bearing potential and male patients whose sexual partners are of child-bearing potential, patients should agree to use an effective method of contraception during the treatment period and for at least 180 days following the last dose of study drugs.

Effective contraceptive measures include: (a) intrauterine device plus one barrier method; (b) oral, implantable or injectable contraceptive plus one barrier method; or (c) tow barrier methods. Effective barrier methods are male or female condoms, diaphragms, and spermicides (cream or gel that contain a chemical to kill sperms).

### **7.5.4. Treatment of isolated lesions.**

Treatment of isolated/symptomatic lesions by local surgery or radiation therapy is permitted for palliative or potentially curative management at any time beyond Cycle 2.

All interventions should be discussed in advance with the Medical Monitor.

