### **6.2. Stopping rules for clinical deterioration**

Clinical deterioration is defined by the clinical condition of the patient has worsened and, in the Investigator's opinion, is attributable to disease progression. Such deterioration is not likely to be reversed with additional administration of Investigational Product and supportive care. The decision to continue or stop treatment should be discussed with the Medical Monitor and documented in the study records.

Events that suggest clinical deterioration include, but not limited to the following:

- Performance status decrease of at least 2 points from baseline
- Skeletal related events defined by the following
  - Pathologic bone fracture in the region of cancer involvement
  - Cancer related surgery to bone
  - Spinal cord or nerve root compression
- Bladder outlet or urethral obstruction
- Development of new central nervous system metastases

- Patients that develop new CNS metastases in the setting of improving baseline disease may have focal radiation, resection, or other local curative procedures performed after consultation with the Medical Monitor.
- If continued study therapy is deemed to offer the patient potential benefit, patients may be allowed to restart study therapy after recovery from symptoms related to the procedure performed (i.e., local edema) and steroid dosing at < 10 mg prednisone/day or equivalent.
- Patients that have locally curative procedures while on study drug and subsequently develop new CNS metastases at a subsequent imaging assessment should discontinue study therapy and enter the follow-up period.
- Or any setting where the initiation of new anti-neoplastic therapy has been deemed beneficial to the patient even in the absence of any such documented clinical events.

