**Table 7. Definition of lesions and imaging modality and their requirement**

Definitions	Description
Measurable lesions	Target lesions that can be measured accurately in at least one dimension (longest diameter to be recorded) as $\geq 20$ mm with conventional techniques, or as $\geq 10$ mm with spiral (helical) computed tomography (CT) scan or two (2) times the reconstruction interval (RI) when using spiral (helical) or multidetector CT, but not less than 10 mm.
Non-measurable lesions	Non-target lesions not classified as measurable lesions (longest diameter $<20$ mm with conventional techniques or $<10$ mm with spiral CT scan) and truly non-measurable lesions. These include bone lesions on BS, effusions, and leptomeningeal disease. Any measurable lesions that were not classified as target lesions will be classified as non-target lesions.
Target lesions	
All measurable lesions up to a maximum of 5 lesions and 2 lesions per organ, representative of all involved organs, are to be identified as target lesions and recorded and measured. Target lesions are to be selected on the basis of their size (those with the longest diameter) and their suitability for accurate repeated measurements (either by imaging techniques or clinically).
 
All lesions other than target lesions (or sites of disease) are to be identified as nontarget lesions and are to be recorded. Measurements of these lesions are not required, but the presence or absence of each is to be noted.

Definitions	Description
	
Longest diameter for target lesions - The sum of the longest diameter for all target lesions (SLD).
 
Complete response - Disappearance of all target lesions.
 
Partial response: At least a 30% decrease in the sum of the longest diameter of target lesions, taking as reference the Screening sum longest diameter.
 
Stable disease: Neither sufficient shrinkage to qualify for partial response nor sufficient increase to qualify for progressive disease.
 
Progressive disease: At least a 20% increase in the sum of the longest diameters of target lesions (with addition of diameters of any newly emergent measurable lesions), taking as reference the smallest sum of the longest diameters (nadir) recorded since screening.
 
UE/ND/NA

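### Local surgery or radiotherapy is allowed after Cycle 2, but no rule says how a treated lesion is scored, so shrinkage from a procedure can be counted as a confirmed response and can lengthen duration of response and PFS

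*Combined protocol and SAP*

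**What the plan says.** **Permission.** Section 7.5.4: "Treatment of isolated/symptomatic lesions by local surgery or radiation therapy is permitted for palliative or potentially curative management at any time beyond Cycle 2". The only condition is: "All interventions should be discussed in advance with the Medical Monitor". Section 6.2 adds a second route: patients with new CNS metastases while baseline disease is improving "may have focal radiation, resection, or other local curative procedures performed after consultation with the Medical Monitor". If continued therapy is judged potentially beneficial, "patients may be allowed to restart study therapy after recovery from symptoms related to the procedure performed".

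**Prohibition.** Section 7.5.1 lists as prohibited: "Any surgery for the management of the patient's disease, unless for life-threatening situations during treatment period". It also prohibits radiation except for local pain relief. Section 7.5.2 permits focal radiotherapy for pain after consultation.

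**Response rules.** Sections 8.3 and 11.3.4 define ORR as confirmed CR or PR over treated patients with measurable disease at baseline. In Appendix 15.4, Table 7, target-lesion CR means that no target lesion remains, and PR is: "At least a 30% decrease in the sum of the longest diameter of target lesions, taking as reference the Screening sum longest diameter". Confirmation is required at least 28 days later. Section 11.3.4 summarises duration of response and PFS by Kaplan-Meier methods.

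**Nearest provision.** The UE code in Table 6 covers a baseline lesion that was not, or could not be, assessed. It does not mention resection or irradiation. The response-evaluable set in 11.2.4 has no exclusion for local treatment. The reference in 7.3 to starting a new therapy governs follow-up after treatment ends, not response or censoring.

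**The concern.** The plan lets a measured lesion be removed or irradiated while the patient stays on HLX06, and then measures response only by whether lesions are absent or smaller. ORR and duration of response are listed secondary endpoints. Section 11.3.4 calls ORR the primary efficacy parameter and adds PFS and tumour-burden plots. In an open-label trial capped at 30 patients (before replacements), one or two misattributed responses would visibly change the activity signal carried into later development.

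The permission also clashes with other passages, so sites may differ in what they do as well as in how they score it.

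**Working it through.** The plan states no ORR, duration or efficacy sample size, so there is no figure of its own to reproduce. The check reads the rules against each other and works through their arithmetic.

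**1. Timing.** A cycle is 4 weeks (7.2), so Cycle 2 ends at 2 × 28 = day 56, about week 8. Scans fall at weeks 8, 16 and 24, then every 12 weeks, regardless of treatment delay (8.3). The 7.5.4 permission therefore opens as the first scan falls due, or later if treatment was delayed. A week-16 PR can be confirmed at week 24, well beyond 28 days. Confirmation does not screen out a resected lesion, which stays absent.

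**2. Effect on the sum of diameters.** If a lesion of diameter d is removed from a baseline sum S and the others are unchanged, the fall is d/S. PR needs d/S ≥ 0.30. For k equal lesions the fall is 1/k:

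| Equal target lesions | Fall if one is removed | Target-lesion reading |
|---|---|---|
| 1 | 100% | CR |
| 2 | 50% | PR |
| 3 | 33.3% | PR |
| 4 | 25% | SD |
| 5 | 20% | SD |

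Unequal example (assumed sizes): 50 mm + 30 mm = 80 mm. Resecting the 30 mm lesion leaves 50 mm, and (80 − 50)/80 = 37.5%, a PR.

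With a single target lesion removed, Table 6 gives overall CR if non-target disease is absent or gone, and PR if it is stable. Either counts towards ORR. Table 6 also means that removing the only non-target lesion turns PR into CR when target lesions are already in CR.

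**3. Effect on ORR.** The number with measurable disease is not given; 20 to 30 is assumed. One patient weighs 1/30 = 3.3 points to 1/20 = 5.0 points. At n = 30 (exact 95% CIs):

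- one drug response: 1/30 = 3.3% (0.1 to 17.2)
- one procedure response added: 2/30 = 6.7% (0.8 to 22.1)
- two added: 3/30 = 10.0% (2.1 to 26.5)

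**4. Effect on duration of response and PFS.** Take 80 mm as the nadir. PD needs 1.20 × 80 = 96 mm. With the 50 mm lesion steady, the other lesion must reach 96 − 50 = 46 mm. If it is resected before then, that PD is never recorded.

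**5. Effect on disease control.** A patient with SD or better at week 8 already counts, and one with PD at week 8 is already PD. Treatment under 7.5.4 changes this only if the week-8 scan was missed or coded UE, or if disease control is read at a later time point, which the plan does not define. Pain radiotherapy under 7.5.1 and 7.5.2 carries no cycle limit and is a small further route.

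**6. Conflicting passages.**

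- 7.5.1 allows disease surgery only in life-threatening situations and radiation only for pain; 7.5.4 allows both with curative intent.
- Tables 6 and 7 make a new lesion PD. The Synopsis (treatment cycle), 3.1, 3.3 and 7.2.2.3 continue treatment only up to progression. Section 6.2 allows restart after a new CNS metastasis.

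**The case against.** **UE could be used.** An assessor may code a resected lesion UE, which makes the overall response UE. That stands: the text is ambiguous and does not compel PR or CR. But nothing instructs the assessor to do so, and an irradiated lesion can still be measured. Appendix 15.4 also cites the RECIST guideline, which was not available here; the gap is shown only for the protocol's own text.

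**Direction and visibility.** A reader might infer that the bias always favours the drug and cannot be detected. The documents do not support this. UE coding could be neutral or adverse. Resecting a stable lesion also lowers the nadir: with 50 mm left, PD needs 0.20 × 50 = 10 mm of growth rather than 0.20 × 80 = 16 mm. Section 11.3.4 provides listings of individual measurements and tumour-burden plots, where an abrupt disappearance would show, and the Medical Monitor is to be consulted beforehand. However, Section 7.5 names medications and transfusions, and 11.3.3 tabulates medications. Neither asks for the treated lesion, procedure and date needed to explain such a change.

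**Disease control.** A reader might infer that it is inflated too. Step 5 shows that it hardly moves.

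**Section 7.2.5.** It might be read as a flat contradiction of 6.2, but its wording is "Disease progression or clinical deterioration that no further benefit from treatment is likely", and the benefit qualifier can apply to progression as well. The firmer conflict is with the unqualified passages listed in step 6.

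**Scale.** With four or more equal target lesions, one removal is not enough, and the plan gives no expected frequency of such procedures. Efficacy is descriptive and the intervals are already wide. All of this stands and limits the importance of the point without closing the gap.

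**Conclusion.** The gap is real. Followed literally, the response rules can turn a locally treated lesion into a confirmed response and can lengthen duration of response and PFS. One to three equal target lesions suffice for ORR, at 3.3 to 5 points per patient. This assumes that 20 to 30 treated patients have measurable disease, that the other lesions are unchanged, and that the treated lesion is scored as absent or smaller rather than UE. How often this would happen cannot be estimated from the documents.

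The MTD and DLT conclusions are untouched. Reconciling 7.5.1 with 7.5.4 would not by itself close the gap, because both sections leave room for pain radiotherapy, which may fall on a target lesion. The rule should be fixed before data are seen, so that single responders in a small open-label trial are not decided case by case.

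**What to change.** Add the following to 8.3, 11.3.4 and Appendix 15.4, and apply it equally to hepatocellular patients scored by mRECIST:

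- After local surgery, ablation or radiotherapy to any target or non-target lesion, that lesion is not evaluable for response, and best overall response uses only assessments before the procedure. PD at another site, or from a new lesion, is still scored as PD.
- Duration of response and PFS are censored at the last scan before the procedure, unless PD was documented first. Lesions treated for symptoms may be close to progression, so this censoring may be informative. One sensitivity analysis should therefore count the procedure as an event. PD seen after a procedure should be listed by patient, since the main analysis censors before it.
- Lesion, procedure and date are recorded on the CRF and listed.

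Separately, reconcile 7.5.1 with 7.5.4. Also reconcile 6.2 with the passages that continue treatment only up to progression and with the classing of new lesions as PD. Which clinical rule should hold is for the sponsor to decide.

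The cost is a few sentences, a CRF entry and a listing. A few patients contribute less follow-up, and response rates may be slightly lower. In particular, a true week-8 PR followed by a procedure before its confirmation scan would not count as confirmed.
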